## 2.6.1.1 Adverse events of special interest / grouping of AEs

There are no AEs of special interest defined in this study.

## 2.6.2 Deaths

Deaths are expected to be rare in this study. In case any deaths are occurring, then these will be listed separately including detailed information of AE leading to death.

## 2.6.3 Laboratory data

The following laboratory tests are performed at all site visits during the study:

Chemistry:

- Potassium
- Creatinine

Haematology:

• Haemoglobin

These laboratory variables and their changes from baseline will be evaluated and summarized using descriptive statistics by visit and treatment arm. There will be two separate baseline values defined for the safety laboratory assessments: the first safety laboratory baseline values will be the ones taken on screening visit 1. The subsequent laboratory results obtained during the screening/run-in period will be compared to these. The second safety laboratory baseline values will be the ones taken at the baseline visit. The subsequent laboratory results obtained during the double-blind treatment period will be compared to these. Laboratory values will also be categorized into low, normal and high according to their reference ranges, and shift tables will be constructed. The reference ranges of all laboratory determinations will be included in the ISF before study start and updated whenever necessary.

Clinically significant laboratory abnormalities and any additional laboratory tests taken for subject safety will be listed and reported in the study report.

Urine pregnancy test will be performed for all female subjects with childbearing potential prior to the PET-scans.

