- 9. Serum creatinine > 1.5 x ULN (upper limit of normal) at any time during the screening/run-in period that persists even after modification of concomitant medication(s).

- 10. Contraindication to neprilysin inhibitor or ARB (such as previous angioedema or known intolerance).
- 11. Susceptibility to severe allergic reactions or known hypersensitivity to the active substances or to any of the excipients.
- 12. Intake of any medication that could affect the outcome of the study, interfere with the evaluation of the results or constitute a health risk for the study subject, as judged by the investigator.
- 13. Positive serology to human immunodeficiency virus antibodies (HIVAgAb), hepatitis C virus antibodies (HCVAb) or hepatitis B surface antigen (HBsAg) in medical history.
- 14. Unwillingness to use adequate methods of contraception while participating in the study and for 3 months after the last administration of the PET tracer.
- 15. Participation in another clinical drug study within 3 months prior to the first study treatment administration of this study.
- 16. Prior participation in an investigational PET study or other medical or occupational exposure to significant doses of ionizing radiation, as judged by the investigator.
- 5.5 Recruitment

The subjects will be recruited from the patient population of the hospital district of Southwest Finland. A description of the possible means of subject recruitment is included in the submission to the Ethics Committee (EC). The recruitment of subjects will start after approvals have been received from the EC and Competent Authority (CA).

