# 5.8 Withdrawal of subjects

Study subjects are free to withdraw from the study at any time without providing a reason. However, the investigator should try to find out the reason and document it on the corresponding CRF page. A subject may also be withdrawn from the study if his/her adherence to the study protocol is not acceptable. A study subject needs to discontinue the study if the investigator considers that continuation in the study would be detrimental to the subjects well-being. The following situations should result in the withdrawal of the subject, unless the investigator considers it safe for the subject to continue in the study, possibly after dose modifications of the study drug or other concomitant medication:

- persistent symptomatic hypotension after randomization;
- serum potassium > 5.2 mmol/l after randomization;
- serum creatinine > 1.5 x ULN after randomization.

If the subject continues in the study, the investigator has to document his/her decision in the source documents and verify continuous subject safety with e.g. repeat BP surveillance and/or laboratory safety measurements during unscheduled visit(s).

Irrespective of the reason for discontinuation, discontinued study subjects should be invited for an unscheduled visit as soon as possible in order to perform final safety assessments (incl. BP, safety laboratory tests and possibly other tests judged necessary by the investigator). The CRFs should be as complete as possible.

If discontinuations occur, the need of recruiting additional subjects to reach the targeted total number of subjects will be considered and carried out as appropriate. Discontinued study subjects are not allowed to re-enter the study.

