8.3.4.3 Renal safety monitoring

The following category of abnormal renal laboratory value has to be considered during the course of the study:

- Serum event:
  - confirmed (after ≥24h) increase in serum creatinine of ≥25% compared to baseline during normal hydration status
- 8.3.4.4 Reporting of study treatment errors including misuse/abuse

Medication errors are unintentional errors in the prescribing, dispensing, administration or monitoring of a medicine while under the control of a healthcare professional, patient or consumer (EMA definition).

Medication errors are usually unintentional, although a patient can intentionally 'commit' a medication error due to a lack of medical knowledge or sound judgment (e.g. intentionally removing drug from capsule and dissolving in juice) or there is an accidental drug omission by an HCP).

Misuse refers to situations where the medicinal product is intentionally and inappropriately used not in accordance with the protocol.

Abuse corresponds to the persistent or sporadic, intentional excessive use of a medicinal product, which is accompanied by harmful physical or psychological effects.

Study treatment errors and uses outside of what is foreseen in the protocol will be collected in the appropriate CRF, irrespective of whether or not associated with an AE/SAE and reported to Safety only if associated with an SAE. Misuse or abuse will be collected and reported in the safety database irrespective of it being associated with an AE/SAE.

Treatment error type	Document in CRF (Yes/No)	Document in AE eCRF	Complete SAE form
Unintentional study treatment error	Yes	Only if associated with an AE	Only if associated with an SAE
Misuse/Abuse	Yes	Yes,	Yes, even if not associated with a SAE

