# 2 Statistical methods

# 2.1 Data analysis general information

The statistical analyses in this study will be conducted by the CRO using SAS 9.4M3. At the raw data generated by electronic data capture (EDC) system will be combined to applicable analysis data sets, as required, and statistical output will be generated based on these aggregated data sets.

All data will be tabulated using summary statistics and/or listed. For continuous data both absolute values and the corresponding changes form baseline will be presented, and the following summary statistics will be included; number of observations, mean, standard deviation, minimum, first quartile, median, third quartile and maximum. In addition gemetric mean and coefficient of variation may be provided in the summaries of efficacy endpoints, as applicable.

Categorical data will be presented as counts and percentages, i.e., n (xx.x%). Changes form baseline in categorical data will be displayed in shift tables. Percentages will be based on the number of subjects in the analysis data set used.

Summary statistics will be presented by randomized treatment group and in total, and by visit and assessment time, as applicable. In addition, summary statistics may be presented by final titrated dose group during run-in period and other stratification factor levels as described in the each section of this document.

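### No planned table counts, by arm and over all post-randomisation values, the subjects who cross the protocol's own creatinine and potassium limits

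*SAP*

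**What the plan says.** Three outputs are planned for potassium, creatinine and haemoglobin in SAP 2.6.3, and the table overview in SAP 5.6 (14.3.4) matches them.

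- Numeric summary: "These laboratory variables and their changes from baseline will be evaluated and summarized using descriptive statistics by visit and treatment arm". SAP 2.1 defines the statistics as "number of observations, mean, standard deviation, minimum, first quartile, median, third quartile and maximum", for values and for changes from baseline.
- Shift tables: "Laboratory values will also be categorized into low, normal and high according to their reference ranges, and shift tables will be constructed".
- Listings: "Clinically significant laboratory abnormalities and any additional laboratory tests taken for subject safety will be listed and reported in the study report".

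Protocol 9.2.7.3 plans the same kind of analysis. SAP 2.6.1.1 adds: "There are no AEs of special interest defined in this study".

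The protocol states numeric limits elsewhere. Section 5.8 gives two criteria for withdrawal unless the investigator judges it safe to continue: "serum potassium > 5.2 mmol/l after randomization", and creatinine above 1.5 x ULN. Section 8.3.4.3 defines a renal event, to be confirmed after at least 24 hours: "increase in serum creatinine of ≥25% compared to baseline during normal hydration status". SAP 2.4.3 repeats the section 5.8 limits when it discusses intercurrent events, but attaches no analysis to them.

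**The concern.** Protocol 2.6 names hyperkalaemia and renal impairment, with hypotension, as the most commonly reported adverse reactions to sacubitril/valsartan, and the protocol sets numeric limits for both. A reader of the study report will want to know how many subjects in each arm crossed those limits. The planned tables do not answer this. They describe the distribution at each visit and movement across the laboratory's reference range, which are different questions.

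Two features make the gap matter. Reference-range categories can hide a large change in creatinine. And the values most likely to cross a limit are often taken at unscheduled visits, whose place in the by-arm tables the SAP leaves unclear. A difference between arms in limit crossings could therefore be hard to see in the planned laboratory tables. If a threshold table is asked for only after unblinding, the definitions will be chosen with the results in view.

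**Working it through.** The documents give no laboratory event rate and no precision target for safety, so there is no stated figure on this point to reproduce. The inputs are the limits above, the entry criterion in protocol 5.4, and 30 enrolled per arm (protocol 9.1).

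**1. Is a count planned anywhere?** SAP 5.6 (14.3.4) has a summary, a shift table and an abnormal-value listing for safety laboratory data. None counts subjects above 5.2 mmol/l, above 1.5 x ULN, or with a rise of at least 25%.

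**2. What can the creatinine shift table show?** The entry exclusion is "Serum creatinine > 1.5 x ULN (upper limit of normal) at any time during the screening/run-in period", and it applies only if this persists after changes to concomitant medication. Values between 1.0 and 1.5 x ULN may therefore enter. Let *b* be the baseline as a multiple of ULN.

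- For *b* above 1.0, every rise is high to high. The rise needed to reach 1.5 x ULN is 1.5/*b* - 1:
  - *b* = 1.1: 1.5/1.1 - 1 = 36.4%. A 25% rise gives 1.1 x 1.25 = 1.375 x ULN.
  - *b* = 1.2: 1.5/1.2 - 1 = 25.0%.
  - *b* = 1.4: 1.5/1.4 - 1 = 7.1%.
- For *b* at or below 1.0, a 25% rise stays normal when 1.25*b* is at most 1.0, that is, when *b* is at most 0.8. At *b* = 0.75 the result is 0.75 x 1.25 = 0.94 x ULN, tabulated normal to normal.
- Between 0.8 and 1.0 x ULN, a 25% rise does cross ULN and shows as a shift.

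**3. What can the numeric summary show?** It includes all these subjects at scheduled visits. As an illustration, suppose *k* of 30 subjects rise by 40% and the rest do not change. The mean percentage change is then *k* x 40/30:

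- *k* = 1: 1.3 points.
- *k* = 3: 4.0 points.

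The largest change appears as the maximum, but a maximum does not say how many subjects crossed a limit. SAP 2.1 and 2.6.3 also mention changes from baseline without mentioning percentage changes, so a 25% criterion cannot be read directly from the table.

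**4. Where are the critical values taken?** Protocol 5.8 invites discontinued subjects to an unscheduled visit for final safety tests, and follows subjects who continue above a limit by repeat measurements at unscheduled visits. Protocol 7.2 calls for an unscheduled visit after a dose change in the first four weeks. The repeat value that confirms the renal event may often be such a test too. SAP 2.6.3 summarises by visit and sends additional safety tests to listings.

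**5. How precise would counts be with 30 per arm?** Exact (Clopper-Pearson) 95% intervals:

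- 0/30: 0 to 11.6%.
- 3/30: 2.1 to 26.5%.
- 6/30: 7.7 to 38.6%.

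**The case against.** A reader might infer that laboratory safety is compared through reference-range shifts alone, and that worsening above ULN cannot appear. The documents do not support this. SAP 2.6.3 with 2.1 also summarises values and changes by visit and arm, with quartiles and maximum. A marked creatinine rise at a scheduled visit enters that summary, diluted and without a subject count.

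It is also tempting to say that many subjects in the lower GFR stratum start above ULN. The documents give no figure for that; they show only that some may.

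Nor can the potassium rate in protocol 2.6 be carried over to this trial. The 19.7% is for values above 5.4 mmol/l, not 5.2. It comes from a much larger trial against enalapril, and the enalapril rate was higher, at 21.1%. It is no evidence of a difference that the tables would hide here. The within-category problem is also shown only for creatinine, because the laboratory's potassium range is not given.

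Four further objections deserve weight.

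- *Unscheduled values.* Protocol 8.3.3 separates the same tests repeated at unscheduled visits from further tests done for safety. The SAP's listing sentence may mean only the latter, and its shift-table sentence is not limited to scheduled visits. This stands: the text is ambiguous and does not state an exclusion.
- *Other routes by arm.* Withdrawal reasons (SAP 2.3.1) and adverse events (SAP 2.6.1) are tabulated by treatment. This stands in part. Protocol 5.8 lets a subject above a limit continue, and protocol 8.3.4 makes a laboratory value an adverse event only if it causes signs or symptoms, is judged clinically significant or needs therapy. Both routes depend on investigator judgement.
- *Derivability.* Protocol Table 3 schedules no confirmatory sample and no hydration assessment, so the full renal definition may not be derivable for everyone. This stands, and the fix allows for it.
- *Preference.* The SAP follows protocol 9.2.7.3, and listings for about 60 subjects can be read one by one. That is fair, but a listing leaves the reader to do the count, without fixed rules.

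**Conclusion.** The point holds as a specific, inexpensive improvement to the safety reporting. It is not an error that invalidates the plan. The protocol states three laboratory limits, and no planned table counts by arm the subjects who cross them over all post-randomisation values. The shift table is uninformative for creatinine worsening from baselines above ULN, and can miss a 25% rise from baselines up to 0.8 x ULN. The by-visit summaries cover scheduled values but give no count.

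This rests on two readings: that results from unscheduled visits may fall outside the by-visit tables, which the SAP does not settle, and that adverse event and withdrawal tables capture a breach only when the investigator acts on it or judges it significant. How many subjects would be affected cannot be estimated from the documents. With about 30 per arm, the counts would describe the arms and would not support a formal comparison.

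**What to change.** Before unblinding, add to SAP 2.6.3 and 5.6 one descriptive table on the safety set, by arm. It should give the number and percentage of subjects whose worst post-randomisation value, scheduled or unscheduled, meets each limit already in the protocol:

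- creatinine rise of at least 25% from the baseline visit, with the subset confirmed by a repeat value after at least 24 hours where one exists;
- creatinine above 1.5 x ULN;
- potassium above 5.2 mmol/l.

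Keep the existing summaries, shift tables and listings. State in a footnote that confirmation and hydration status may not be available for every subject.

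The cost is one extra table, built from potassium and creatinine results already collected. It changes no clinical rule, sample size or significance level. The SAP addendum added covariance analyses for ten further imaging parameters, so one safety table is a proportionate addition.

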# 2.6.4 Other safety data

# 2.6.4.1 Vital signs

The actual values of systolic and diastolic blood presure (BP) and heart rate (HR) and their changes from baseline will be evaluated with descriptive statistics by treatment arm. There will be two separate baseline values defined for the BP and HR measurements: the first BP and HR baseline value will be the one taken on the first screening visit. The subsequent BP and HR measurements during the screening/run-in period will be compared to this. The subsequent BP and HR measurements during the double-blind treatment period will be compared to this.

# 2.7 Pharmacokinetic endpoints

NA

2.8 PD and PK/PD analyses

NA

2.9 Subject-reported outcomes

NA

# 2.10 Biomarkers

Biomarkers will be measured to understand the potential mechanisms of how sacubitril/valsartan changes myocardial efficiency. Blood samples will be obtained for measurement of NT-proBNP hs-troponin and creatinine to assess effects of interventions on hemodynamics before randomization and repeatedly on visit 3, after 6 weeks of stable sacubitril/valsartan or valsartan treatment.

These biomarkers will be summarized using descriptive statistics including levels at baseline and Visit 3, and change from baseline at Visit 3. Creatinine is collected as a safety laboratory parameter at all visits as described in Section 2.6.3, and will thus be summarized as part of safety laboratory. In addition NT-proBNP will be analysed by an ANCOVA according to description under secondary endpoints (Section 2.5.1). A shift table corresponding to those for safety lab will be provided.

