### Statistical methods:

The study hypothesis is that short-term therapy with sacubitril/valsartan added on standard HF therapy improves cardiac efficiency in patients with systolic HF. Analysis of covariance (ANCOVA) will be used for statistical analysis, when appropriate. Other statistical analyses may also be implemented, as described in the statistical analysis plan (SAP).

Efficacy: The difference in the primary (cardiac efficiency) and exploratory efficacy parameters will be evaluated by comparing change from baseline at visit 3 between treatment groups. Change from baseline will be analysed using an ANCOVA, adjusting for treatment, strata, and baseline. From this model the treatment difference will be estimated with a 95% confidence interval (CI). In addition, treatment by stratification interaction analyses will be performed for the primary efficacy parameters in order to estimate within stratification group differences.

Safety: AEs reported during the study will be classified by system organ class (SOC) and preferred terms (PT) using the MedDRA coding system. The number and proportion (%) of subjects' AEs will be presented by treatment and dose level and the severity and causality will be tabulated with subject and event counts. Systolic and diastolic BP and HR and laboratory safety variables and their changes from the baseline values will be evaluated and summarized using descriptive statistics by treatment and dose level. The laboratory values tabulated as low, normal or high according to their reference ranges and clinically significant laboratory abnormalities will be listed.

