# Exploratory Endpoints

The changes in the following cardiac and systemic hemodynamics parameters will be evaluated as exploratory efficacy endpoints: EF, NT-proBNP, systemic BP, SVR, coronary vascular resistance and cardiac oxygen consumption. The change from baseline in these parameters after 6 weeks on stable sacubitril/valsartan or valsartan therapy will be analyzed by an ANCOVA including treatment and stratification as independent factors and covariate adjustment for baseline cardiac efficiency. From this model, the within treatment group (sacubitril/valsartan-valsartan) changes will be estimated by least square means and the corresponding treatment difference between treatments will be calculated with a 95% confidence interval and p-value. For both the baseline visit and visit 3, the results will be also summarized using descriptive statistics, with the visit 3 results to be summarized also by dose level and treatment arm.

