# 2.5.2 Statistical hypothesis, model, and method of analysis

The change from baseline in these parameters after 6 weeks on stable sacubitril/valsartan or valsartan therapy will be analyzed by an ANCOVA including treatment and stratification as

| Novartis | Confidential | Page 18 of 30          |
|----------|--------------|------------------------|
| SAP      |              | Study No. CLCZ696BFI03 |

independent factors and covariate adjustment for baseline cardiac efficiency. From this model, the within treatment group changes will be estimated by least square means and the corresponding treatment difference (sacubitril/valsartan-valsartan) will be calculated with a 95% confidence interval and p-value.

Descriptive statistics will be provided for these secondary endpoints by treatment arm including levels at each visit and change from baseline.

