#### 1.1 Amendment(s) of the SAP

As SAP states: analyses for Viable myocardium energetic efficiency will be done using the same approach as is applied for the primary endpoint. For this reason, a summary statistic by strata and an ANCOVA model is added, where the treatment by strata interaction will be evaluated. Based on this model, the within stratum treatment difference will be estimated.

Regarding secondary endpoints. The SAP did not include ANCOVA models for the following parameters:

- Resting perfusion (PET)
- Viable myocardium resting perfusion (PET)
- Viable myocardium clearance rate (PET)
- Left ventricle mass (Echocardiography)
- Stroke volume (Echocardiography)
- Cardiac output (Echocardiography)
- Left ventricular mechanical work (SBP echocardiography x SV x HR)/ LV mass (Echocardiography)
- Global Longitudinal Strain (Echocardiography)
- Left ventricular systolic volume (Echocardiography)
- Left ventricular diastolic volume (Echocardiography)

Additional ANCOVA models will be added according to description under secondary endpoints: The change from baseline in these parameters after 6 weeks on stable sacubitril/valsartan or valsartan therapy will be analyzed by an ANCOVA including treatment and stratification as independent factors and covariate adjustment for baseline. From this model, the within treatment group changes will be estimated by least square means and the corresponding treatment difference (sacubitril/valsartan-valsartan) will be calculated with a 95% confidence interval and p-value.

SAP addendum Version: 1.0 Date: 04/07/2022 Sponsor: Novartis Finland Oy Study Code: CLCZ696BFI03 NCT No.: 2017-002113-64

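### NT-proBNP is to be analysed as an untransformed change adjusted for baseline cardiac efficiency, other sections say only baseline, and a log-scale model on its own baseline would probably be more precise

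*SAP*

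**What the plan says.** SAP 2.10 does not describe a model for NT-proBNP. It points elsewhere: "In addition NT-proBNP will be analysed by an ANCOVA according to description under secondary endpoints", with a reference to Section 2.5.1. That section only lists the endpoints and two derivations; the model is in 2.5.2.

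SAP 2.5.2 gives one model for six endpoints: EF, NT-proBNP, systemic BP, systemic vascular resistance, coronary vascular resistance and k_mono.

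- Response: "The change from baseline in these parameters after 6 weeks on stable sacubitril/valsartan or valsartan therapy will be analyzed by an ANCOVA". No transformation is named.
- Terms: treatment and stratification as "independent factors and covariate adjustment for baseline cardiac efficiency".

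Protocol 9.2.6 (Exploratory Endpoints) lists the same endpoints and has the same model: "ANCOVA including treatment and stratification as independent factors and covariate adjustment for baseline cardiac efficiency".

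Two places word the covariate differently. The protocol synopsis, covering primary and exploratory parameters together, says "Change from baseline will be analysed using an ANCOVA, adjusting for treatment, strata, and baseline". The SAP addendum adds models for ten PET and echocardiography parameters and presents them as following the secondary-endpoint description, but writes "including treatment and stratification as independent factors and covariate adjustment for baseline", without naming cardiac efficiency. NT-proBNP is not one of the ten.

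On geometric statistics, SAP 2.1 says "In addition gemetric mean and coefficient of variation may be provided in the summaries of efficacy endpoints". That is optional and concerns descriptive summaries, not the model.

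**The concern.** There are two separate faults.

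The first is the covariate. Baseline cardiac efficiency is the right covariate for the primary endpoint. For NT-proBNP it is the baseline of a different variable. Subtracting the baseline to form a change is not the same as adjusting for it: unless the correlation between visits is perfect, regression to the mean leaves part of any baseline imbalance in the treatment difference. Adjusting for efficiency removes only the part that efficiency happens to predict. The fault applies to every endpoint in SAP 2.5.2 except where the wording is overridden, and the conflicting texts leave the programmer to choose.

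The second is the scale. NT-proBNP is a positive concentration. If it is right-skewed and treatment acts roughly in proportion, a few subjects with high baselines dominate the absolute changes. The interval is then wide, and a real proportional reduction can be missed. At stake is a supporting mechanistic result: NT-proBNP is the only one of the three listed biomarkers to receive a model, an interval and a p-value.

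**Working it through.** **What the documents supply.** The plan's only power calculation is for cardiac efficiency (SAP 3, Protocol 9.1): a 15% change, CV 19.7%, two-sided 5%, 80% power, 27 per arm. It reproduces:

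n = 2 × (1.960 + 0.842)² × (19.7 / 15)² = 2 × 7.849 × 1.725 = 27.08 per arm.

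This says nothing about NT-proBNP. It only supplies the 27 per arm used below.

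**What has to be assumed.** Lognormal NT-proBNP, log-SD σ, log-scale correlation ρ between baseline and visit 3, and a multiplicative treatment effect. The documents give none of these, so a range is shown.

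**Simulated power, 27 per arm, no strata**

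| σ | ρ | True reduction | Raw change, baseline efficiency (SAP 2.5.2) | Raw change, own baseline | Log change, own log baseline |
|---|---|---|---|---|---|
| 0.7 | 0.9 | 25% | 68% | 81% | 92% |
| 0.9 | 0.8 | 25% | 23% | 30% | 47% |
| 0.3 | 0.8 | 15% | 82% | not run | 90% |

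**A separate simulation with three binary strata**, 3,000 trials per setting, 27 per arm, splits the two changes fully:

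| σ | ρ | True reduction | Raw, efficiency | Raw, own | Log, efficiency | Log, own |
|---|---|---|---|---|---|---|
| 0.8 | 0.8 | 25% | 30% | 39% | 51% | 55% |
| 1.0 | 0.8 | 25% | 18% | 22% | 35% | 38% |
| 1.2 | 0.9 | 25% | 17% | 23% | 45% | 47% |
| 0.9 | 0.85 | 15% | 12% | 14% | 22% | 23% |
| 0.3 | 0.8 | 15% | 80% | 86% | 86% | 89% |
| 0.9 | 0.85 | none | 5.0% | 4.8% | 5.9% | 5.6% |

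The last row is type I error, close to 5% for all four models. The assumed correlation between NT-proBNP and efficiency hardly matters: at 0 and at −0.6 the SAP model has 28% and 29% power (σ 0.9, ρ 0.85, 25% reduction).

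**Closed-form check of the log model.** Residual SD = σ√(1 − ρ²), SE = SD × √(2/27), power ≈ Φ(|ln ratio| / SE − 1.96).

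- σ 0.7, ρ 0.9: SD 0.305, SE 0.0830; 0.2877 / 0.0830 = 3.46; power Φ(1.50) = 93%.
- σ 0.9, ρ 0.8: SD 0.540, SE 0.147; 0.2877 / 0.147 = 1.96; power Φ(0.00) = 50%.
- σ 0.3, ρ 0.8, ratio 0.85: SD 0.180, SE 0.0490; 0.1625 / 0.0490 = 3.32; power Φ(1.36) = 91%.

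These are 1 to 3 points above the simulated 92%, 47% and 90%, as expected from using a normal in place of a t distribution.

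**Equivalent sample size** = [(z of new power + 1.96) / (z of old power + 1.96)]².

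- 68% to 92%: (3.365 / 2.428)² = 1.9.
- 23% to 47%: (1.885 / 1.221)² = 2.4.
- 82% to 90%: (3.242 / 2.875)² = 1.3.

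**Which change does the work.** At a 25% reduction, changing the covariate on the raw scale gains 81 − 68 = 13 and 30 − 23 = 7 points in the first table, and 9, 4 and 6 in the second. Once the response is logged, own baseline adds 4, 3 and 2 points. Most of the gain comes from the log scale.

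**Size of the imbalance problem.** A log-scale change without own-baseline adjustment carries a share (1 − ρ) of the baseline imbalance. With σ 0.9 and ρ 0.8, an imbalance of one standard error is 0.9 × √(2/27) = 0.245. The share left in is 0.2 × 0.245 = 0.049, about 5% in the ratio, against an effect of 0.288.

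**The case against.** The strongest reply is that the covariate wording is a slip. The synopsis and the addendum both say baseline, and the addendum claims to restate the secondary-endpoint description, so own baseline may always have been intended. The fair comparator would then be raw change on own baseline, and the gap narrows from 68% against 92% to 81% against 92%, and from 23% against 47% to 30% against 47%. This stands in part. It shows a conflict to be reconciled, for all the endpoints in SAP 2.5.2. It does not settle the matter, because the two sections that govern NT-proBNP both name cardiac efficiency and the addendum does not cover it.

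Second, the untransformed scale is inferred from silence. That is correct. It is still the ordinary reading of a change from baseline, and the text offers no other.

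Third, a reader might infer that the log model is much more precise at no cost. The documents do not support that. They give no distribution for NT-proBNP, and the simulated data obey the log model's own assumptions. At low skew or with a small effect the gain is modest. There is also a price: the target changes from a difference in mean change, in concentration units, to a ratio of geometric means, and the two intervals cannot be compared directly.

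Fourth, a reader might take NT-proBNP for the main biomarker offered to explain the primary result. Protocol 8.2.3 and SAP 2.10 list it with hs-troponin and creatinine. It is the only one modelled, but it is exploratory, with no imputation and no power claim.

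**Conclusion.** The point holds in limited form. The governing text adjusts NT-proBNP for baseline cardiac efficiency, names no transformation, and conflicts with the synopsis and the addendum. That much rests on the documents alone.

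The size of the loss rests on assumed lognormal values and a proportional effect. For log-SDs of 0.7 to 0.9 and a 25% reduction, the change to a log model with own baseline is worth roughly 1.9 to 2.4 times the sample size; at log-SD 0.3 and a 15% reduction it is worth about 1.3 times. Type I error is near nominal either way, so the plan's test is not invalid, only likely to be inefficient.

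Nothing here touches the primary analysis or its conclusion. The practical risk is that an imprecise NT-proBNP interval is read as absence of a natriuretic-peptide effect.

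**What to change.** Before unblinding:

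1. Reconcile the covariate wording in the protocol synopsis, Protocol 9.2.6, SAP 2.5.2 and the SAP addendum, so that each exploratory endpoint, NT-proBNP included, is adjusted for its own baseline.
2. For NT-proBNP, analyse log(visit 3) minus log(baseline) by ANCOVA with treatment, the stratification factors and log baseline NT-proBNP. Report the ratio of geometric means with its 95% confidence interval.
3. Correct the reference in SAP 2.10 from 2.5.1 to 2.5.2.

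The cost is a few lines of text and one derived variable. Baseline NT-proBNP is already collected, and the model has no more parameters than now. The change of estimand should be stated openly. If the blind has already been broken, the log analysis should be shown beside the planned one and labelled as added afterwards. No change is needed for hs-troponin, which is only summarised and for which geometric means are already allowed.
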